# 8.3.3.2 RELATIONSHIP TO STUDY INTERVENTION

All adverse events (AEs) must have their relationship to study intervention assessed by the clinician who examines and evaluates the participant based on temporal relationship and his/her clinical judgment. The degree of certainty about causality will be graded using the categories below. In a clinical trial, the study product must always be suspect.

- **Related** The AE is known to occur with the study intervention, there is a reasonable possibility that the study intervention caused the AE, or there is a temporal relationship between the study intervention and event. Reasonable possibility means that there is evidence to suggest a causal relationship between the study intervention and the AE.
- Not Related There is not a reasonable possibility that the administration of the study intervention caused the event, there is no temporal relationship between the study intervention and event onset, or an alternate etiology has been established.

# 8.3.3.3 EXPECTEDNESS

The principal investigator will be responsible for determining whether an adverse event (AE) is expected or unexpected. An AE will be considered unexpected if the nature, severity, or frequency of the event is not consistent with the risk information previously described for the study intervention.

# 8.3.4 TIME PERIOD AND FREQUENCY FOR EVENT ASSESSMENT AND FOLLOW-UP

The principal investigator and investigators on the study will review labs and vitals continuously and as outlined in the protocol. The patients are monitored in a critical care unit; as per standard of care, vitals are documented and monitored continuously. The occurrence of an adverse event (AE) or serious adverse event (SAE) may come to the attention of study personnel during the course of treatment.

All AEs including local and systemic reactions not meeting the criteria for SAEs will be captured on the appropriate case report form (CRF). Information to be collected includes event description, time of onset, clinician's assessment of severity, relationship to study product (assessed only by those with the training and authority to make a diagnosis), and time of resolution/stabilization of the event. All AEs

occurring while on study must be documented appropriately regardless of relationship. All AEs will be followed to adequate resolution.

Any medical condition that is present at the time that the participant is screened will be considered as baseline and not reported as an AE. However, if the study participant's condition deteriorates at any time during the study, it will be recorded as an AE.

Changes in the severity of an AE will be documented to allow an assessment of the duration of the event at each level of severity to be performed. AEs characterized as intermittent require documentation of onset and duration of each episode.

The study coordinator will record all reportable events with start dates occurring any time after informed consent, during hypothermic protocol and through full rewarming. The principal investigator will review all AE and SAE in a timely manner to determine severity and relation to study intervention.

# 8.3.5 ADVERSE EVENT REPORTING

AE will be reported to local IRB per Northwell Health Policy and procedure within 5 business days of event. The Principal Investigator is responsible for accurate and timely reporting of adverse events in the source document and case report forms. All investigators and study coordinators are responsible for recording all new clinical experiences, exacerbations and/or deterioration of an existing clinical condition occurring after the subject has been enrolled in the study on the appropriate case report form. They will also provide follow up on the adverse events until a resolution or an appropriate end point is reached.

### 8.3.6 SERIOUS ADVERSE EVENT REPORTING

The study investigator shall complete an Unanticipated Adverse Device Effect Form and submit to the study sponsor and to the reviewing Institutional Review Board (IRB) as soon as possible, but in no event later than 10 working days after the investigator first learns of the effect. The study sponsor is responsible for conducting an evaluation of an unanticipated adverse device effect and shall report the results of such evaluation to the Food and Drug Administration (FDA) and to all reviewing IRBs and participating investigators within 10 working days after the sponsor first receives notice of the effect. Thereafter, the sponsor shall submit such additional reports concerning the effect as FDA requests.

According to 21 CFR 312.64(b), a principal investigator must report to the sponsor, here the Department of Cardiothoracic Surgery, any serious adverse event, whether or not considered related to the hypothermic protocol, the study intervention, including those listed in the protocol and must include an assessment of whether there is a reasonable possibility that the study intervention caused the event. AE as defined in *Section 8.3.2* will be reported in accordance to the local rules and regulations of local IRB reporting structure and will be reported to the Department leadership. These AEs will be reported at set time points to the DSMB (at enrollment of 3 subjects, 10, 15 and 20 subjects; four set time points.) We will pause after subject enrollment 3 and present to the DSMB. We will wait for the DSMB to assess safety and determine if enrollment should continue.

Furthermore, according to 21 CFR 312.32(c)(2), the sponsor and investigator must notify FDA of any unexpected fatal or life-threatening suspected adverse reaction as soon as possible but in no case later than 7 calendar days after the sponsor's initial receipt of the information.

# 8.3.7 REPORTING EVENTS TO PARTICIPANTS

AEs and SAEs will be reported to the DSMB established for this study per the data safety monitoring plan and the subjects' LAR will be contacted and informed of the event on an individual basis. Under current circumstances of the COVID-19 pandemic, families and LARs of patients are unable to enter the hospital facility to visit with patients and see clinicians in person. Therefore, daily communication and updates are provided to LAR over the telephone. AEs and SAEs will be reported to the participants' LAR on a daily basis as these patients remain critically ill and daily updates are important.

# 8.3.8 EVENTS OF SPECIAL INTEREST

N/A

# 8.3.9 REPORTING OF PREGNANCY

N/A

# 8.4 UNANTICIPATED PROBLEMS

# 8.4.1 DEFINITION OF UNANTICIPATED PROBLEMS (UP)

The Office for Human Research Protections (OHRP) considers unanticipated problems involving risks to participants or others to include, in general, any incident, experience, or outcome that meets all of the following criteria:

- Unexpected in terms of nature, severity, or frequency given (a) the research procedures that are described in the protocol-related documents, such as the Institutional Review Board (IRB)-approved research protocol and informed consent document; and (b) the characteristics of the participant population being studied;
- Related or possibly related to participation in the research ("possibly related" means there is a reasonable possibility that the incident, experience, or outcome may have been caused by the procedures involved in the research); and
- Suggests that the research places participants or others at a greater risk of harm (including physical, psychological, economic, or social harm) than was previously known or recognized.

This definition could include an unanticipated adverse device effect, any serious adverse effect on health or safety or any life-threatening problem or death caused by, or associated with, a device, if that effect, problem, or death was not previously identified in nature, severity, or degree of incidence in the investigational plan or application (including a supplementary plan or application), or any other unanticipated serious problem associated with a device that relates to the rights, safety, or welfare of subjects (21 CFR 812.3(s)).

# 8.4.2 UNANTICIPATED PROBLEM REPORTING

The investigator will report unanticipated problems (UPs) to the reviewing Institutional Review Board (IRB) and to the Data Safety Monitoring Board. The UP report will include the following information:

- Protocol identifying information: protocol title and number, Pl's name, and the IRB project number;
- A detailed description of the event, incident, experience, or outcome;

- An explanation of the basis for determining that the event, incident, experience, or outcome represents an UP;
- A description of any changes to the protocol or other corrective actions that have been taken or are proposed in response to the UP.

To satisfy the requirement for prompt reporting, UPs will be reported using the following timeline:

- UPs that are serious adverse events (SAEs) will be reported to the IRB and to the study sponsor (Department of Cardiothoracic Surgery) within 24 hours or one (1) business day of the investigator becoming aware of the event.
- Any other UP will be reported to the IRB and to the study sponsor within three (3) business days of the investigator becoming aware of the problem.
- All UPs should be reported to appropriate institutional officials (as required by an institution's written reporting procedures), the supporting agency head (or designee), and the Office for Human Research Protections (OHRP) within three (3) business days of the IRB's receipt of the report of the problem from the investigator.

An investigator shall submit to the sponsor (Department of Cardiovascular and Thoracic Surgery) and to the reviewing Institutional Review Board (IRB) a report of any unanticipated adverse device effect occurring during an investigation as soon as possible, but in no event later than 10 working days after the investigator first learns of the effect (21 CFR 812.150(a)(1)), A sponsor who conducts an evaluation of an unanticipated adverse device effect under 812.46(b) shall report the results of such evaluation to the Food and Drug Administration (FDA) and to all reviewing IRB's and participating investigators within 10 working days after the sponsor first receives notice of the effect. Thereafter the sponsor shall submit such additional reports concerning the effect as FDA requests (21 CFR 812.150(b) (1)).

Any unanticipated problems related or possibly related to use of the Arctic Sun 5000® machine will also be reported to the Biomedical Engineering Department for review and reporting back to the manufacturer. Per the Biomedical Equipment Management Plan, internal quality checks will be initiated.

# 8.4.3 REPORTING UNANTICIPATED PROBLEMS TO PARTICIPANTS

Unanticipated problems will be reported to the DSMB established for this study. The Principal Investigator will determine the need to withdraw the subject from the study for subjects' safety. The subjects' LAR will be contacted and informed of the event on an individual basis. These events will be shared with the DSMB and reported to the IRB of record. At the termination of the study, unanticipated problems will be reported on an aggregate level in the context of a descriptive statistical analysis and manuscript write up.

# 9 STATISTICAL CONSIDERATIONS

# 9.1 STATISTICAL HYPOTHESES

Primary Efficacy Endpoint(s): (1) Decrease in metabolic rate to 10% during and after hypothermic period as compared to baseline metabolic requirement, (2) Increase in oxygen levels during and after hypothermia as compared to baseline oxygen levels, (3) Decrease in carbon dioxide levels during and after hypothermia as compared to baseline carbon dioxide levels

• Secondary Efficacy Endpoint(s): Decreased inflammatory markers (CRP, ESR, D-Dimer, Ferritin) during and after hypothermia as compared to baseline

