# Continue hypothermia

•Perform indirect calorimetry, arterial blood gas, CRP, ESR, D-Dimer, Ferritin

•CBC, basic metabolic profile, magnesium, phosphorus, coagulation profile to be drawn q12 hours during hypothermia.

•Perform indirect calorimetry, arterial blood gas, CRP, ESR, D-Dimer, Ferritin prior to rewarming

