# **3** OBJECTIVES AND ENDPOINTS

OBJECTIVES	ENDPOINTS	JUSTIFICATION FOR ENDPOINTS
Primary		
To determine if the application of mild hypothermia will decrease the patient's metabolic demand and improve carbon dioxide and oxygenation levels	
 
(1) Changes in resting metabolic rate during and after hypothermia
 
(2) Changes in arterial pO2 during and after hypothermia
 
(3) Changes in arterial pCO2 levels during and after hypothermia
 
	Resting metabolic rate is considered the gold standard way to measure metabolic demand. Arterial pO2 and pCO2 are the accepted measurements for oxygen and carbon dioxide levels.
Secondary		
To determine if the application of mild hypothermia reduces the pro- inflammatory response to COVID- 19	Changes in CRP, ESR, D-Dimer, Ferritin, during and after hypothermia.	CRP, ESR, D-Dimer, and Ferritin are inflammatory markers that are have been demonstrated to be elevated in patients with COVID-19 and have been correlated to severity of disease

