### 4 STUDY DESIGN

### 4.1 OVERALL DESIGN

The hypothesis of this study is that the application of mild hypothermia to patients with COVID-19 will decrease their metabolic rate and improve their oxygen and carbon dioxide levels. This is a single site pilot study of 20 subjects. Subjects will be placed on therapeutic hypothermia for 48 hours. Changes in metabolic rate, and levels of oxygen and carbon dioxide will be compared before, during, and after hypothermia.

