## 4.2 SCIENTIFIC RATIONALE FOR STUDY DESIGN

Therapeutic hypothermia is routinely used in patients post cardiac arrest and in patients with cerebral edema secondary to a neurological injury. It has, however, not been used in patients with COVID-19. This study is therefore designed as a small scale pilot study in order to evaluate the feasibility and design of the study and the possible efficiency of hypothermia on COVID patients.

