#### **6** STUDY INTERVENTION

#### 6.1 STUDY INTERVENTION(S) ADMINISTRATION

#### 6.1.1 STUDY INTERVENTION DESCRIPTION

Determination of metabolic rate by the metabolic cart (noninvasive connection of the device to the ventilator for 20 minutes). Initiate hypothermia (established Northwell hypothermia status post cardiac arrest protocol) using the Arctic Sun. Gel pads will be placed on subject body to cover at least 40% of body surface area. The inner layer of gel pad is made up of a heat conductive hydrogel that changes temperature and sticks to the skin. The middle layer of the pad has channels through which water is circulated and the outer layer is designed to insulate the circulating water, allowing it to maintain a temperature. Using sterile technique, a clinician will insert a temperature probe into subjects' bladder. The machine essentially is a cooling blanket. Many clinicians would use ice bags to cool patients, however using the machine allows for more accurate temperature monitoring and precision with the cooling process. The Arctic Sun 5000® is set to a temperature of 34.5 C to lower the body temperature.

Duration of hypothermia will be 48 hours after which the subject will be rewarmed. Metabolic rate, or indirect Calorimetry, will be assessed at baseline, day 1 of hypothermia, day 2 of hypothermia before rewarming, and after full rewarming. CBC, basic metabolic profile, magnesium, phosphorus, coagulation profile, ABG, inflammatory markers would be drawn every 12 hours during hypothermia until subject has achieved full rewarming and once after full rewarming.

The entire hypothermia procedure will last 48 hours. The length of time it takes to cool the patient is a maximum of 3 hours. Once the desired temperature is reached that temperature will be maintained as tolerated by subject. The new temperature of 36.5C will be manually entered into the machine initiating re-warming. Acceptable rewarming range is a temperature of 36.5C to 37.5C. The subject body temperature rewarming is typically set over 6-8 hours. Therefore, the final 6-8 hours of the 48 hour time period is set to rewarm the subject.

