# 7 STUDY INTERVENTION DISCONTINUATION AND PARTICIPANT DISCONTINUATION/WITHDRAWAL

### 7.1 DISCONTINUATION OF STUDY INTERVENTION

Discontinuation from hypothermia protocol does not mean discontinuation from the study, and remaining study procedures should be completed as indicated by the study protocol. If a clinically significant finding is identified (including, but not limited to changes from baseline) after enrollment, the investigator or qualified designee will determine if any change in participant management is needed. Any new clinically relevant finding will be reported as an adverse event (AE).

The data to be collected at the time of study intervention discontinuation will include the following:

- Vitals including blood pressure, heart rate and temperature, indirect Calorimetry
- Labs as outlined in the SoA- CBC, magnesium, BMP, phosphorus, ABG, coagulation panel (coags) and inflammatory markers
- Ventilatory Settings- oxygen percentage, respiratory rate setting, tidal volume and positive end expiratory pressure (PEEP)

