# 9.4.2 ANALYSIS OF THE PRIMARY EFFICACY ENDPOINT(S)

The metabolic rate, p02, and pCO2 during each time point after induction of hypothermia will be compared to baseline using the Wilcoxon rank sum test.

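### Sections 9.4.2 and 9.4.3 apply an unpaired test to before-and-after data from the same patients, and the only numerical target, in 9.1, is worded unclearly and never used

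*Combined protocol and SAP*

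**What the plan says.** **Target.** Section 9.1 gives for metabolic rate "Decrease in metabolic rate to 10% during and after hypothermic period as compared to baseline metabolic requirement". For pO2, pCO2 and the inflammatory markers it gives a direction only. The Section 3 table has no threshold: "Changes in resting metabolic rate during and after hypothermia". The synopsis and Section 4.1 have none either, and Section 9.2 is marked not applicable.

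**Design.** There is one group of 20 patients, whose metabolic rate, oxygen and carbon dioxide "will be compared before, during, and after hypothermia" (Section 4.1).

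**Analysis.** Under Section 9.4.2, metabolic rate, pO2 and pCO2 "during each time point after induction of hypothermia will be compared to baseline using the Wilcoxon rank sum test". Section 9.4.3 uses the same test for the inflammatory markers. Neither section states a significance level, a main time point, or how the three primary variables combine into one conclusion.

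**Time points.** Section 6.1.1 schedules calorimetry at baseline, then "day 1 of hypothermia, day 2 of hypothermia before rewarming, and after full rewarming". Blood gases are drawn every 12 hours during cooling and once after rewarming.

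**Interim review.** Section 9.4.6 marks interim analyses as not applicable. Section 10.1.2 nevertheless lists efficacy, futility and having met the primary endpoint among circumstances that may justify termination, and Section 10.1.6 has the DSMB assess efficacy as well as safety data.

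**The concern.** The rank sum test compares two independent samples. Here every baseline value has a partner from the same patient. The test discards that link, so differences between patients count as noise even though they cancel in each patient's own change. Its reference distribution is then too wide and real effects are more easily missed. In a pilot meant to inform further work, a result of no effect could reflect the choice of test.

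The target adds a second gap. A decrease *to* 10% of baseline and a decrease *by* 10% are very different claims, and the analysis refers to neither. Because no time point is named as the main one, the same results could be reported as supporting or not supporting the hypothesis.

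**Working it through.** **1. The target.** A fall to 10% of baseline leaves 10%, so the fall is 100 − 10 = 90%. A fall by 10% leaves 90%. The documents contain no second statement of the figure to settle which is meant.

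**2. Number of comparisons.** From the daily columns of the Schedule of Activities: 3 variables × 3 later days (Days 2, 3 and 4) = 9. From Section 6.1.1: 3 calorimetries plus 4 or 5 blood gases for each of pO2 and pCO2, so 3 + 4 + 4 = 11 or 3 + 5 + 5 = 13. The blood-gas count depends on whether rewarming falls inside or after the 48 hours; Section 6.1.1 says both.

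**3. True size of the planned test.** The documents give no significance level or correlation; assume two-sided 5% and correlation r between baseline and follow-up. The variance of the difference in means is 2σ²(1 − r)/n, while an unpaired test assumes 2σ²/n. In the normal approximation the rejection rate under no effect is therefore 2Φ(−1.96/√(1 − r)):

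- r = 0.3: 1.96/0.837 = 2.34, giving 1.9%
- r = 0.5: 1.96/0.707 = 2.77, giving 0.6%
- r = 0.7: 1.96/0.548 = 3.58, giving 0.03%

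Simulating the rank sum test itself at n = 20 gives 2.1%, 0.8% and 0.1%. The signed-rank test stays near 5%.

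**4. Power for a true 10% fall.** Assumed: n = 20, normal values, baseline mean 100, the same coefficient of variation (CV) at both times, two-sided 5%, 10,000 simulated trials per cell.

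| CV | r | Rank sum | Signed-rank |
|---|---|---|---|
| 15% | 0.5 | 52% | 78% |
| 15% | 0.7 | 54% | 95% |
| 20% | 0 | 32% | 31% |
| 20% | 0.5 | 27% | 53% |
| 20% | 0.7 | 24% | 76% |
| 20% | 0.9 | 20% | over 99% |
| 25% | 0.5 | 16% | 39% |
| 25% | 0.7 | 11% | 56% |

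Repeat runs agree to within a point or two. Over CV 15–30% and r 0.3–0.7, signed-rank power runs from about 20% to 95%.

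**5. What n = 20 can say about 10%.** The SD of change is roughly CV × √(2(1 − r)), in percent of the baseline mean, and the 95% half-width is 2.093 × SD/√20. At CV 20%:

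- r = 0.5: SD = 20.0, half-width 2.093 × 20.0/4.472 = 9.4 points
- r = 0.7: SD = 15.5, half-width 7.3 points
- r = 0.9: SD = 8.9, half-width 4.2 points

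For the whole interval to lie beyond 10%, the observed fall must exceed 10 plus the half-width, that is 14.2 to 19.4 points here. If the true fall is exactly 10%, this happens in about 2.5% of trials, by construction of the interval.

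**6. Several endpoints.** If any one of three endpoints at one time point counts as success, three independent correctly sized 5% tests give 1 − 0.95³ = 14.3% false positives. If all three must succeed, no adjustment across endpoints is needed. Correcting the test without naming a main time point would expose the wider problem: unadjusted signed-rank tests over 9 to 13 comparisons give at least one false positive in 21–42% of simulated trials.

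**The case against.** The best defence is the study's purpose: a "small scale pilot study in order to evaluate the feasibility and design of the study and the possible efficiency of hypothermia" (Section 4.2). That excuses the missing power calculation and makes elaborate confirmatory machinery a matter of preference. It does not excuse an unpaired test on paired data, since the plan does state hypotheses and test them.

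Further points on the other side have weight:

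- **Detection.** A reader might infer that a paired analysis would nearly always show a 10% fall. That needs high correlation, around 0.75 or more, and the documents give none. At zero correlation pairing gains nothing.
- **False positives.** A reader might infer that the planned test produces them. Each single comparison errs the other way. Only if any one of the 9 to 13 results counted as success would the planned test's overall rate rise: to 16–21% at correlation 0.3, and still only 1–2% at 0.7.
- **Combination of endpoints.** The primary objective joins lower metabolic demand and better gas levels with *and*. If all three must succeed, a multiplicity correction across endpoints is unnecessary.
- **Target.** A reader might infer that the trial cannot address its own target. Section 9.4.1 examines changes and Section 9.4.8 lists individual data, so the percent change can be calculated. What is missing is an agreed figure and a stated way of reading the result. A fall to 10% of baseline is implausible, so a wording slip is the likely explanation.
- **Interim looks.** A reader might infer inflated error from repeated efficacy looks. The schedule of 3, 10, 15 and 20 subjects in Section 8.3.6 is for adverse events, the wording of 10.1.2 is permissive, and the DSMB charter is not yet written. No error rate can be claimed.

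**Conclusion.** The choice of test is wrong as written in Sections 9.4.2 and 9.4.3, whatever the variances. Its direction is clear whenever repeated values in a patient are positively correlated: the test is too conservative and usually loses power. The size is not known. In the illustration at CV 20% the loss runs from nothing at zero correlation, through about half the attainable power at 0.5 (27% against 53%), to most of it at 0.9. CV, correlation, normality and the 5% level are all assumptions.

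The target in 9.1 needs the sponsor's confirmation and a role in the analysis, and one main time point should be named. The disagreement of 10.1.2 and 10.1.6 with 9.4.6 is real but secondary, with no demonstrated effect on the results. These points should be corrected before analysis. They do not show that the trial would reach a false positive conclusion.

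**What to change.** 1. **Sections 9.4.2 and 9.4.3:** replace the rank sum test with the Wilcoxon signed-rank test on within-patient change, using percent change for metabolic rate. Report the paired estimate with a 95% CI.
2. **Section 9.1:** the sponsor confirms the threshold and corrects the wording (if confirmed, a decrease by 10% from baseline). Report the percent change and its CI against that figure, and state that 20 patients serve to estimate the fall and are not expected to establish a fall of at least 10%.
3. **Main time point:** name one. A candidate already in the Section 1.2 schema is "Perform indirect calorimetry, arterial blood gas, CRP, ESR, D-Dimer, Ferritin prior to rewarming". First reconcile the two statements in 6.1.1 on whether rewarming falls inside or after the 48 hours. Treat other time points as supportive. State whether all three endpoints must succeed (no adjustment across them) or any one is enough (then adjust, for example with Holm).
4. **Missing values:** report how many patients have no value at the main time point. Section 7.1 already collects, at discontinuation of the intervention, "Vitals including blood pressure, heart rate and temperature, indirect Calorimetry" and blood gases. Show these values as a sensitivity analysis, with the temperature recorded. Patients withdrawn from the study under 7.2 may have none.
5. **Sections 10.1.2, 10.1.6 and 9.4.6:** reconcile them, either by removing the efficacy and futility grounds (including that of having met the primary endpoint) or by defining the looks and criteria.

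The cost is wording only; no new data are needed. The downside is that fewer time points carry a confirmatory reading.
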